8.3. Pharmacokinetic Analyses

8.3.1. Overview of Planned Pharmacokinetic Analyses

The pharmacokinetic (PK) analyses will be based on the “Pharmacokinetic” population, unless otherwise specified.

Table 5 provides an overview of the planned analyses with full details being presented in Appendix 11.10: List of Data Displays.

Table 5 Overview of Planned Pharmacokinetic Analyses

Endpoints	Untransformed				Log-Transformed			
	Summary		Individual		Summary		Individual	
	F	T	F	L	F	T	F	L
Plasma Drug Concentrations	Y ²³	Y ³	Y ¹	Y				
Derived PK Parameters		Y ³		Y		Y ³		

NOTES :

- T = Table, F = Figures, L = Listings, Y = Yes display generated.
- Stats Analysis = Represents TFL related to any formal statistical analyses (i.e. modelling) conducted.
- Summary = Represents TFL related to any summaries (descriptive statistics) of the observed raw data.
- Individual = Represents FL related to any displays of individual subject observed raw data.

1. Linear and Semi-Log plots will be created on the same display.
2. Mean (Linear and Semi-Log on same display) and Median (Linear and Semi-Log on same display) plots will be created.
3. Displays generated using the “PK” populations.

8.3.2. Drug Concentration Measures

Refer to [Appendix 4](#): Data Display Standards & Handling Conventions (Section [11.4.2](#) Reporting Process & Standards).

8.3.3. Pharmacokinetic Parameters

8.3.3.1. Deriving Pharmacokinetic Parameters

- Refer to [Appendix 4](#): Data Display Standards & Handling Conventions (Section [11.4.2](#) Reporting Process & Standards).

- The pharmacokinetic parameters will be calculated by standard non-compartmental analysis according to current working practices and using Phoenix Win Nonlin.
- All calculations of non-compartmental parameters will be based on actual sampling times.
- Pharmacokinetic parameters described in [Table 6](#) will be determined from the plasma GSK1070806 concentration-time data, as data permits.
- Any deviation from the planned analyses will be described in detail in the study report.

Table 6 **Derived Pharmacokinetic Parameters**

Parameter	Parameter Description
AUC(0-t)	Area under the concentration-time curve until the last time point of PK sample. Partial AUCs such as over 7, 30 or 90 days may be generated if deemed necessary.
Cmax	Maximum observed concentration, determined directly from the concentration-time data.
tmax	Time to reach Cmax, determined directly from the concentration-time data.
Lamda_z	Terminal phase rate constant The number of points to determine Lambda_z The first point used to determine Lambda_z The last point used to determine Lambda_z
t½	Apparent terminal half-life will be calculated as: $t\frac{1}{2} = \ln 2 / \text{Lambda}_z$
AUC(0-∞)	Area under the concentration time curve from predose to infinity.

NOTES:

- Additional parameters may be included as required.

9. OTHER STATISTICAL ANALYSES

9.1. Overview of Planned Pharmacokinetic / Pharmacodynamic Analyses

The pharmacokinetic / pharmacodynamic (PK/PD) analyses will be based on the “All Subjects” population, unless otherwise specified.

For the other biomarker variables/PD endpoints, summary tables will be reviewed to identify those biomarker variables/PD endpoints where there is a potential trend. If there is a trend then exploratory plots (scatter plots) will be presented for individual and/or pooled plasma GSK1070806 concentrations versus corresponding biomarker variables/PD endpoints (e.g. IL-18, IP-10).

- [Table 7](#) provides an overview of the planned PK/PD analyses with further details of data displays being presented in Appendix 11.10: List of Data Displays. Any deviation from the planned analyses or additional analyses performed based on emerging data will be described in detail in the study report.

Table 7 **Overview of Planned PK/PD Analyses**

Endpoints	Absolute			
	Summary		Individual	
	F	T	F	L
Serum IL-18 (drug bound, total or free) vs. PK Plasma Concentrations	Y			

Endpoints	Absolute			
	Summary		Individual	
	F	T	F	L

NOTES :

- T = Table, F = Figure, L = Listing, Y = Yes display generated.
- Stats Analysis = Represents TFL related to any formal statistical analyses (i.e. modelling) conducted.
- Summary = Represents TFL related to any summaries (descriptive statistics) of the observed raw data
- Individual = Represents FL related to any displays of individual subject observed raw data.

11. APPENDICES

Section	Appendix
RAP Section 4 : Analysis Populations	
Section 11.1	Appendix 1 : Protocol Deviation Management and Definitions for Per Protocol Population
RAP Section 5 : General Considerations for Data Analyses & Data Handling Conventions	
Section 11.2	Appendix 2 : Time and Events
Section 11.3	Appendix 3 : Treatment States & Phases
Section 11.4	Appendix 4 : Data Display Standards & Handling Conventions 
 • Study Treatment & Sub-group Display Descriptors • Baseline Definitions & Derivations • Reporting Process & Standards
Section 11.5	Appendix 5 : Derived and Transformed Data 
 • General, Study Population & Safety • Efficacy • Pharmacokinetic • Pharmacodynamic / Biomarkers
Section 11.6	Appendix 6 : Premature Withdrawals & Handling of Missing Data 
 • Handling of Missing Dates • Handling of Partial Dates
Section 11.7	Appendix 7 : Values of Potential Clinical Importance 
 • Laboratory Values • ECG's • Vital Signs
Other RAP Appendices	
Section 11.8	Appendix 8 : Abbreviations & Trade Marks
Section 11.9	Appendix 9 : List of Data Displays
Section 11.10	Appendix 10 : Example Mock Shells for Data Displays

11.1. Appendix 1: Protocol Deviation Definitions for Per Protocol Population**11.1.1. Exclusions from Per Protocol Population**

A subject meeting any of the following criteria will be excluded from the Per Protocol population:

Number	Exclusion Description
01	Subject takes prohibited Concomitant Medications
02	Others as defined in the PDMP

NOTES: For the details for prohibited concomitant medications, please refer to protocol Section 6.11.2

11.2. Appendix 2: Time and Events

Study Day ¹	Screening	Pre-operative (baseline)	Intra-operative (D0) ¹	4-8h ²	D1	D2	Daily until discharge	Discharge	D30	D90	6 & 12 months ¹³	Unscheduled Visit
Informed Consent/Demographics	X											
Medical/drug/alcohol/tobacco history	X											
GSK1070806 IV Infusion			←-----→ ¹⁵									
Kidney preservation fluid IL-18			X ¹⁶									
Kidney biopsy (post-reperfusion) ³			X (~45 min)									
Clinical biopsy reports (if applicable)			←-----→									
Concomitant medication	X	X	X ¹⁷	X	X	X	X	X	X	X	X	X
Evidence of infection	X			X	X	X	X	X	X	X	X	X
SAE / AE monitoring			←-----→									
DGF status (up to day 7)				←-----→								
Urine output		X (native output)	X	X	X	X	X					
Dialysis events since last assessment		X		X	X	X	X	X	X	X	X	X
Graft survival			←-----→									
Viral serology (recipient & donor – HIV, Hep B/C, EBV) ⁴	X ⁵	X									X	X
Viral serology (recipient & donor -herpes, varicella) ⁴		X										
CMV monitoring	X ⁵	X									X	X
BK virus monitoring ⁶		X							X	X	X	X
Vital signs ⁷	X			X	X	X	X	X	X	X	X	X
Complete physical	X										X	X
12-lead ECG	X							X			X	X
Hematology / Clinical Chemistry / Urinalysis	X			X	X	X	X	X	X	X	X	X
Pregnancy test ⁸	X								X	X	X	X
Serum cytokines / PD biomarkers		X ¹¹	X (~45 min at biopsy)	X	X	X		X	X	X	X	X

Study Day ¹	Screening	Pre-operative (baseline)	Intra-operative (D0) ¹	4-8h ²	D1	D2	Daily until discharge	Discharge	D30	D90	6 & 12 months ¹³	Unscheduled Visit
Free, GSK1070806 bound & total IL18 ⁹		X ¹¹	X (~45 min at biopsy)	X	X	X		X	X	X	X	X
Pharmacokinetics ^{9,10}		X ¹¹	X (~45 min at biopsy)	X	X			X (@168 hrs or at earlier discharge)	X	X	X	X
Immunogenicity ¹²		X ¹¹							X	X	X	X
Urinary biomarkers		X ¹¹		X	X	X	X	X	X	X	X	X
Peripheral blood leucocyte flow phenotyping ¹⁴		X						X		X	X	
PBMCs frozen for in vitro stimulation assays ¹⁴		X						X		X	X	
PBMCs placed in trizol for transcriptomic analysis ¹⁴		X						X		X	X	

1. Day 0 defined as the calendar day of transplant.
2. Time post reperfusion.
3. Biopsies during transplantation may be 'core or wedge' at the discretion of the operating surgeon. If, in the judgement of the operating surgeon, biopsy poses unwarranted risk to the patient, it may be omitted.
4. Viral serology will include HIV, HBsAg, anti-HBc, anti-HBs antibodies, and hepatitis C antibody (if hepatitis C antibody positive, a hepatitis C RIBA immunoblot or polymerase chain reaction assay should be reflexively performed on the same sample to confirm the results as per NHS standard procedure), and serology for herpes simplex virus, Epstein Barr virus, and varicella zoster virus.
5. Screening viral status may be the most recent value recorded in the patient's medical records.
6. If BK positive then follow up screening should be implemented.
7. Vital signs will include systolic and diastolic blood pressure, pulse rate, and temperature.
8. Pregnancy testing will be performed in women of childbearing potential. Screening test may be urine or serum.
9. Sampling time points may be adjusted as appropriate based on emerging data.
10. PK sampling time points are as follows: predose, 45 min to 1 hr into infusion (coinciding with biopsy), 4-8 hrs, 24 hrs, 168 hrs (or pre-discharge if discharge before day 7), day 30 day 90, 6 and 12 months. Exact PK sampling time is to be recorded.
11. Blood and urine samples for immunogenicity and biomarker analyses must be collected prior to infusion with GSK1070806
12. For any non-completer a serum sample for immunogenicity testing will be taken 12 mths post-operatively.
13. For subjects who withdraw from study, where possible, assessments should continue according to the Time and Events table. The 6 and 12 mth safety follow-up should be performed.
14. **Samples for subjects from Cambridge site only.**
15. GSK1070806 can be infused any time during the pre-operative and/or intra-operative periods, but infusion must be complete prior to reperfusion of the allograft.

16. Sample to be obtained at time of back-table allograft preparation.
17. Documentation of anaesthetics excluded.

11.3. Appendix 3: Treatment States and Phases

11.3.1. Treatment Phases

Assessments and events will be classified according to the time of occurrence relative to study treatment, unless otherwise specified.

Treatment Phase	Definition
Pre-Treatment	Date/Time \leq Study Treatment Start Date/Time
Post-Treatment	Date /Time $>$ Study Treatment Stop Date/Time

Treatment Description

Code	Treatment Description	Final Data Display (i.e. HARP/other)
A	3 mg/kg GSK1070806	3 mg/kg GSK1070806

11.3.2. Treatment States

Assessments and events will be classified according to time of occurrence relative to the start and/or stop date/time of the study treatment.

11.3.3. Treatment States for AE Data

Treatment State	Definition
AE = Pre-Treatment	AE Start Date/Time $<$ Study Treatment Start Date/Time
AE Onset Time Since 1 st Dose (Days)	If Treatment Start Date/Time $>$ AE Onset Date/Time : = AE Onset Date - Treatment Start Date If Treatment Start Date \leq AE Onset Date : = AE Onset Date – Treatment Start Date + 1 Missing otherwise
AE Duration (Days)	AE Resolution Date/Time – AE Onset Date/Time (follow SOP)
AE = Drug-related	If relationship is marked 'YES' on [Inform/CRF OR value is missing.

NOTES:

- If the study treatment stop date is missing then the AE will be considered to be On-Treatment

11.4. Appendix 4: Data Display Standards & Handling Conventions

11.4.1. Baseline Definition & Derivations

11.4.1.1. Baseline Definitions

For all endpoints baseline value will be the latest pre-dose assessment.

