2.5. Definition of Renal Graft Function

Primary Non Function:

- Permanent lack of function of the allograft defined as an inability to discontinue dialysis from the time of transplantation. Note: The study site will decide whether patients have primary non function DGF or not and record it in data set.

3 day Functional Delayed Graft Function:

- <10% fall in SCr versus baseline per day averaged over first 3 days with OR without dialysis

7 day Functional Delayed Graft Function:

- <30% reduction in baseline SCr in first 7 days with OR without dialysis

3 day Intermediate Graft Function:

- 10- 20% fall in SCr versus baseline per day averaged over first 3 days without dialysis

7 day Intermediate Graft Function:

- 30-70% reduction in baseline Cr in first 7 days without dialysis

3 day Immediate Graft Function:

- >20% fall in SCr versus baseline per day averaged over first 3 days without dialysis

7 day Immediate Graft Function:

- >70% reduction in baseline Cr during the first 7 days without dialysis

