11.4.1.2. Derivations and Handling of Missing Baseline Data

Definition	Reporting Details
Change from Baseline	= Post-Baseline Visit Value – Baseline
[% Change from Baseline]	= [(Post-Baseline Visit Value – Baseline) / Baseline] x 100]

NOTE :

- Unless otherwise specified, the baseline definitions specified in [11.4.1.1Baseline Definitions](#) will be used for derivations for endpoints / parameters and indicated on summaries and listings.
- Unless otherwise stated, if baseline data is missing no derivation will be performed and will be set to missing.
- The baseline definition will be footnoted on all change from baseline displays.

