11.7. Appendix 7: Values of Potential Clinical Importance

11.7.1. Laboratory Values

Haematology				
Laboratory Parameter	Units	Category	Clinical Concern Range	
			Low Flag (< x)	High Flag (>x)
Hematocrit	Ratio of 1	Male		0.54
		Female		0.54
		Δ from BL	↓0.075	
Hemoglobin	g/L	Male		180
		Female		180
		Δ from BL	↓25	
Lymphocytes	GI/L		0.8	
Neutrophil Count	GI/L		1.5	
Platelet Count	GI/L		100	550
White Blood Cell Count (WBC)	GI/L		3	20

Clinical Chemistry				
Laboratory Parameter	Units	Category	Clinical Concern Range	
			Low Flag (< x)	High Flag (>x)
Albumin	G/L		30	
Calcium	mmol/L		2	2.75
Creatinine	umol/L	Δ from BL		↑ 44.2
Glucose	mmol/L		3	9
Magnesium	mmol/L		0.5	1.23
Phosphorus	mmol/L		0.8	1.6
Potassium	mmol/L		3	5.5
Sodium	mmol/L		130	150
Total CO ₂	mmol/L		18	32

Liver Function			
Test Analyte	Units	Category	Clinical Concern Range
ALT/SGPT	IU/L	High	≥ 2x ULN
AST/SGOT	IU/L	High	≥ 2x ULN
AlkPhos	IU/L	High	≥ 2x ULN
T Bilirubin	µmol/L	High	≥ 1.5xULN
T. Bilirubin + ALT	µmol/L U/L	High	1.5xULN T. Bilirubin + ≥ 2x ULN ALT

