11.9.6. Safety Tables

Safety Tables					
No.	Population	IDSL / TST ID / Example Shell	Title	Programming Notes	Deliverable
Adverse Events – Overall					
3.01	All Subjects	AE1	Summary of All Adverse Events		IA1, IA2, SAC
3.02	All Subjects	AE3	Summary of Common Adverse Events by Preferred Term	Common AE = Frequency > 1%	IA1, IA2, SAC
3.03	All Subjects	AE1	Summary of Drug-Related Adverse Events by System Organ Class		IA1, IA2, SAC
3.04	All Subjects	AE1	Summary of Serious Adverse Events by System Organ Class		IA1, IA2, SAC
3.05	All Subjects	AE1	Summary of Adverse Events Leading to Withdrawals from Study or Study Treatment		IA1, IA2, SAC
Adverse Events – in patients (before discharge)					
3.06	All Subjects	AE1	Summary of All Adverse Events before Discharge		IA2, SAC
3.07	All Subjects	AE3	Summary of Common Adverse Events by Overall Frequency before Discharge		IA2, SAC
3.08	All Subjects	AE5	Summary of Drug-Related Adverse Events by System Organ Class before Discharge		IA2, SAC

Safety Tables					
No.	Population	IDSL / TST ID / Example Shell	Title	Programming Notes	Deliverable
3.09	All Subjects	AE1	Summary of Serious Adverse Events by System Organ Class before Discharge		IA2, SAC
3.10	All Subjects	AE1	Summary of Adverse Events Leading to Withdrawals from Study / Permanent Discontinuation of Study Treatment before Discharge		IA2, SAC
Adverse Events – out patients (after discharge)					
3.11	All Subjects	AE1	Summary of All Adverse Events after Discharge		IA2, SAC
3.12	All Subjects	AE3	Summary of Common Adverse Events by Overall Frequency after Discharge		IA2, SAC
3.13	All Subjects	AE5	Summary of Drug-Related Adverse Events by System Organ Class after Discharge		IA2, SAC
3.14	All Subjects	AE1	Summary of Serious Adverse Events by System Organ Class after Discharge		IA2, SAC
3.15	All Subjects	AE1	Summary of Adverse Events Leading to Withdrawals from Study / Permanent Discontinuation of Study Treatment after Discharge		IA2, SAC
Labs					
3.16	All Subjects	LB1	Summary of Chemistry Changes from Baseline		IA2, SAC

Safety Tables					
No.	Population	IDSL / TST ID / Example Shell	Title	Programming Notes	Deliverable
3.17	All Subjects	LB1	Summary of Emergent Chemistry Results of Potential Clinical Importance		IA1, IA2, SAC
3.18	All Subjects	LB1	Summary of Haematology Changes from Baseline		IA2, SAC
3.19	All Subjects	LB1	Summary of Emergent Haematology of Potential Clinical Importance		IA1, IA2, SAC
Vital Signs					

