11.9.10. ICH Listings

ICH Listings					
No.	Population	IDSL / TST ID / Example Shell	Title	Programming Notes	Deliverable
Subject Disposition					
1	All Subjects	ES2	Listing of Reasons for Study Withdrawal		IA1, IA2, SAC
2	All Subjects	ES7	Listing of Reasons for Screening Failure		IA1, IA2, SAC
3	All Subjects	SA3a	Listing of Subjects Excluded from Any Populations		IA2, SAC
4	All Subjects	DV2	Listing of Important Protocol Deviations		IA1, IA2, SAC
5	All Subjects	IE3	Listing of Subjects with Inclusion/Exclusion Criteria Deviations		IA1, IA2, SAC
Demographics					
6	All Subjects	DM2	Listing of Demographic Characteristics		IA1, IA2, SAC
7	All Subjects	DM9	Listing of Race		IA1, IA2, SAC
Exposure					

ICH Listings					
No.	Population	IDSL / TST ID / Example Shell	Title	Programming Notes	Deliverable
8	All Subjects	EX3	Listing of Exposure		SAC
Adverse Events					
9	All Subjects	AE7	Listings of Subject Numbers for Individual Adverse Events		IA1, IA2, SAC
10	All Subjects	AE8	Listing of All Adverse Events		IA1, IA2, SAC
11	All Subjects	AE8	Listing of Serious Adverse Events		IA1, IA2, SAC
12	All Subjects	AE8	Listing of Adverse Events Leading to Withdrawal from Study		IA1, IA2, SAC
LABS					
13	All Subjects	LB5	Listing of Haematology Laboratory Data for Subjects with Abnormalities of Potential Clinical Importance		IA1, IA2, SAC
14	All Subjects	LB5	Listing of Clinical Chemistry Laboratory Data for Subjects Abnormalities of Potential Clinical Importance.		IA1, IA2, SAC
15	All Subjects	UR2b	Listing of Urinalysis Data		IA2, SAC

CONFIDENTIAL

204824

ICH Listings					
No.	Population	IDSL / TST ID / Example Shell	Title	Programming Notes	Deliverable
16	All Subjects	Non-Standard SAFE_L1	Listing of Clinical Chemistry Laboratory Values (Total cholesterol, HDL, LDL, Triglycerides, Creatinine Clearance (MDRD) and Associated Ratios).		IA2, SAC
ECGs					
17	All Subjects	EG3	Listing of ECG Values for Subjects with Abnormalities of Potential Clinical Importance.		IA1, IA2, SAC
Vital Signs					
18	All Subjects	CP_VS4	Listing of Vital Signs for Subjects with Abnormalities of Potential Clinical Importance		IA1, IA2, SAC
Immunogenicity					
19	All Subjects	IMM2	Listing of Immunogenicity Results	ADA tiers	IA2, SAC

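### The only creatinine flag of potential clinical importance is measured from the pre-transplant value, so later deterioration of a well-recovered graft will usually not be flagged in Table 3.17 or Listing 14

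*SAP*

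**What the plan says.** The creatinine row of the clinical chemistry table in SAP section 11.7.1 reads "Creatinine umol/L Δ from BL ↑ 44.2". The figure stands in the high-flag column, and the row has no absolute limit. Potassium, sodium, phosphorus and total CO2 in the same table do have absolute limits.

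Baseline is set in SAP section 11.4.1.1: "For all endpoints baseline value will be the latest pre-dose assessment". Section 11.4.1.2 carries this into all derivations ("Unless otherwise specified, the baseline definitions specified in" that section apply), and no exception is made for the creatinine flag. A footnote to the Time and Events table (SAP section 11.2) says that the "infusion must be complete prior to reperfusion of the allograft".

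SAP section 2.5 describes what a working graft does to the pre-dose value. Intermediate function is "30-70% reduction in baseline Cr in first 7 days without dialysis". Immediate function is ">70% reduction in baseline Cr during the first 7 days without dialysis".

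The flag feeds two displays, both due at IA1, IA2 and SAC: Table 3.17, "Summary of Emergent Chemistry Results of Potential Clinical Importance", and Listing 14, "Listing of Clinical Chemistry Laboratory Data for Subjects Abnormalities of Potential Clinical Importance". Note 2 to Table 4 (SAP section 8.2.1) ties the chemistry summaries to the PCI criteria.

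**The concern.** A change-from-baseline flag works when baseline is the level from which deterioration should be judged. Here that holds only until the graft starts to work. From then on the reference is a level the subject has left behind, and the better the recovery, the further creatinine must climb before it is flagged. The rule is therefore least sensitive in the subjects with the best early result.

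Clinical laboratory values are a stated safety endpoint, and chemistry is scheduled to 12 months. Table 3.17 is where a reader would look for the number of subjects with an emergent creatinine abnormality, in a trial whose target organ is the kidney. A low count after discharge could be read as reassurance when it mostly reflects the choice of reference.

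The SAP departs from the pre-dose value elsewhere. For the creatinine half-life, section 8.1.2 starts DGF patients from the value after dialysis has finished. A post-transplant reference for creatinine is therefore not foreign to the plan.

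**Working it through.** The SAP has no figure of its own to reproduce here: 44.2 umol/L is set, not derived. The check is how far creatinine must rise after recovery before it is flagged.

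**Inputs**
- Increment: 44.2 umol/L above baseline (section 11.7.1).
- Reference B: the latest pre-dose creatinine (section 11.4.1.1), always before reperfusion (footnote in section 11.2).
- Fractional fall f: 0.30 and 0.70 are the boundaries in section 2.5; 0.50 is a midpoint.
- Size of B: not in the SAP. Assumed to lie between 300 and 1000 umol/L.

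**Formulas**
- Flag limit = B + 44.2
- Lowest value after recovery (nadir) = (1 − f) × B
- Rise from nadir needed to flag = f × B + 44.2
- Multiple of nadir needed = (B + 44.2) / ((1 − f) × B)

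**Results** (umol/L; the last column is the multiple of nadir)

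| B | Flag limit | Fall | Nadir | Rise needed | Multiple |
|---|---|---|---|---|---|
| 300 | 344.2 | 30% | 210 | 134.2 | 1.64 |
| 300 | 344.2 | 50% | 150 | 194.2 | 2.29 |
| 300 | 344.2 | 70% | 90 | 254.2 | 3.82 |
| 600 | 644.2 | 30% | 420 | 224.2 | 1.53 |
| 600 | 644.2 | 50% | 300 | 344.2 | 2.15 |
| 600 | 644.2 | 70% | 180 | 464.2 | 3.58 |
| 1000 | 1044.2 | 30% | 700 | 344.2 | 1.49 |
| 1000 | 1044.2 | 50% | 500 | 544.2 | 2.09 |
| 1000 | 1044.2 | 70% | 300 | 744.2 | 3.48 |

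**Is a doubling from nadir flagged?** It is if 2 × (1 − f) × B exceeds B + 44.2, that is, if (1 − 2f) × B exceeds 44.2.
- f = 0.50 or more: the left side is zero or negative, so a doubling is not flagged at any B.
- f = 0.30: the condition is 0.4 × B > 44.2, or B > 110.5, so a doubling is flagged throughout the assumed range.

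**One case.** With B = 700 and a 70% fall, the nadir is 0.3 × 700 = 210. A later rise to 630 is three times the nadir, but the change from baseline is 630 − 700 = −70 and there is no flag. The flag needs more than 744.2.

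**Same increment measured from the nadir.** After a 70% fall the limit would be 134.2, 224.2 and 344.2 for B = 300, 600 and 1000, against 344.2, 644.2 and 1044.2 under the rule as written.

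**The case against.** A reader might infer that a graft which recovers and then fails can never be flagged. The SAP does not support that:
- Any value more than 44.2 umol/L above the pre-dose value is flagged. For B between 300 and 1000 that is an excess of 14.7% down to 4.4% of B, which could occur if the pre-dose value was low, for instance soon after dialysis.
- After a modest recovery the rule still works: a doubling after a 30% fall is flagged.
- Table 3.17 and Listing 14 cover all chemistry analytes. A subject with a failing graft can enter through potassium, phosphorus, total CO2 or another analyte with absolute limits.

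Nor is late deterioration hidden. Figures 2.01 and 2.02 plot each subject's creatinine, and Listing 22 lists it without a PCI filter. Figure 2.04 shows graft survival, Table 2.24 dialysis independence to 12 months, and Tables 2.09 and 2.10 biopsy-proven rejection. With at most 30 subjects, individual plots can be read one by one.

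It can also be said that section 11.7.1 specifies a rise from baseline, and nothing shows that a rise from nadir was ever meant. That is right: this is a poorly chosen reference, not an internal contradiction. The existing row also has a use. A subject whose creatinine climbs without dialysis is not a primary-endpoint event but would be flagged.

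All of this stands, and it limits the consequence. It does not supply what is missing: none of those displays counts subjects whose creatinine rose by a stated amount after recovery. The individual plots also leave out unscheduled visits (section 11.4.2).

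**Conclusion.** The point holds in a limited form. The rule as written makes the count of emergent creatinine abnormalities insensitive to deterioration after good recovery. Over the assumed baselines of 300 to 1000 umol/L, creatinine must reach about 3.5 to 3.8 times its nadir after a 70% fall and 2.1 to 2.3 times after a 50% fall. After a 30% fall it must reach about 1.5 to 1.6 times.

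The defect itself follows from sections 11.4.1.1, 11.7.1 and 11.2. Its size rests on the assumed baselines, since the SAP gives none. That these values reflect end-stage disease is an inference from the transplant setting.

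The gap lies in one flag and the two displays built on it. It does not affect the primary endpoint or any efficacy result, and it does not mean that late graft failure goes unreported. It is worth correcting because the flag concerns the trial's target organ and a low count would be easy to misread.

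**What to change.** Keep the existing creatinine row in Appendix 7 and add a second one, for reporting only: a rise of more than 44.2 umol/L above the subject's lowest earlier post-transplant creatinine. Only values taken after the last recorded dialysis event up to that time are eligible as the reference, or any post-transplant value if the subject has not been dialysed since transplant. Where no eligible earlier value exists, only the existing row applies. Show the two rows separately in Table 3.17 and Listing 14, and footnote the reference for each.

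The cost is one row, one derived reference value and one footnote. The Time and Events table already schedules chemistry and dialysis events after transplant, so no new data are needed.

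There are limits. A running minimum over daily inpatient samples will produce more flags, some of them transient, and a value taken soon after dialysis may be a low reference. The reference restarts if dialysis resumes, so return to dialysis must be read from the dialysis displays. Under section 11.4.2, declines seen only at unscheduled visits would still appear only in listings.

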2.2. Study Objective(s) and Endpoint(s)

Objectives	Endpoints
Primary	Primary

 To assess the frequency of delayed graft function (DGF) in donation after circulatory death (DCD) renal transplant recipients treated with GSK1070806. 	
 Proportion of subjects requiring dialysis during the first 7 days post transplant, (excluding requirement for dialysis due to hyperkalemia within first 24 post-operative hours).
Secondary	Secondary

 To assess graft function in DCD renal transplant recipients treated with GSK1070806. 	
 Serum creatinine at baseline and over time post transplant. Urine output at baseline and over time post transplant. Proportion of subjects in the first 7 days with: 
 Primary Non Function Functional DGF Intermediate Graft Function Immediate Graft Function

 To assess the effect of GSK1070806 on acute rejection risk, and rejection/PD biomarkers. 	
 Proportion of subjects with episodes of biopsy-proven acute rejection. Rejection biomarkers/ PD markers (including serum IP-10 and Mig) at baseline and over time post transplant.

 To assess the effect of GSK1070806 on dialysis dependency and graft survival. 	
 Number of dialysis events per patient in the first 30 days post transplant. Proportion of subjects who are dialysis-independent at visits up to 12 months post transplant.

 To assess the safety and tolerability of GSK1070806 in renal transplant recipients. 	
 AEs and SAEs 
 Clinical laboratory values Vital signs Frequency, type and severity of infections

 To assess the pharmacokinetics of GSK1070806 in renal transplant recipients. 	
 Serum concentrations of GSK1070806 over time, and derived pharmacokinetic parameters if feasible (AUC, Cmax).

Objectives	Endpoints

 To assess the effect of GSK1070806 administration on serum IL-18 levels. 	
 Free, total, and GSK1070806 bound IL-18 at baseline and over time post transplant.

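### The only scheduled pre-dose creatinine is the screening value, so the baseline for the secondary graft-function classes may predate pre-operative dialysis

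*SAP*

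**What the plan says.** One baseline rule covers everything (section 11.4.1.1): "For all endpoints baseline value will be the latest pre-dose assessment". Creatinine has no rule of its own, and nothing says how a baseline sample should stand in time to dialysis before surgery.

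The schedule in Appendix 2 (section 11.2) has a pre-operative column that it labels as baseline. The row "Hematology / Clinical Chemistry / Urinalysis" is marked at Screening, blank in that column, blank intra-operatively, and marked from 4-8 h onward. The row "Dialysis events since last assessment" is blank at Screening and marked in the pre-operative column. The same column carries serum biomarkers, IL-18, PK and immunogenicity samples. Note 11 adds: "Blood and urine samples for immunogenicity and biomarker analyses must be collected prior to infusion with GSK1070806". Chemistry is not named there.

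Several secondary analyses need a baseline creatinine. Section 2.2 lists "Serum creatinine at baseline and over time post transplant". Section 2.5 sets the graft-function classes by percentage fall. For example, 3-day functional DGF is "<10% fall in SCr versus baseline per day averaged over first 3 days with OR without dialysis", and 7-day functional DGF is a less than 30% "reduction in baseline SCr in first 7 days with OR without dialysis". The intermediate and immediate classes are also percentage falls from baseline, and both require no dialysis.

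**The concern.** The schedule and the baseline rule do not fit together. The column labelled as baseline has no creatinine, so the rule falls back on screening. If a patient is dialysed between the screening sample and surgery, dialysis lowers creatinine and the later comparison counts that drop as graft function. If creatinine rises after screening, a real fall is understated.

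The outputs at stake are the 3-day and 7-day functional, intermediate and immediate classes (Table 2.08), creatinine change from baseline, and the creatinine half-life in non-DGF patients, whose starting value under section 8.1.2 is the baseline. With no control arm, there is no comparison group in which the same shift would show. Table 2.08 and the creatinine change-from-baseline table are also first-interim (IA1) deliverables.

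**Working it through.** **Which creatinine is baseline.** The chemistry row, set against the 12 column heads, gives two candidates around dosing: Screening and 4-8 h. Note 2 to the schedule times the 4-8 h sample from reperfusion, and note 15 requires the infusion to be complete before reperfusion. The 4-8 h sample is therefore post-dose, which leaves Screening as the only scheduled pre-dose value.

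**Whether another value may count.** Section 11.4.2 keeps unscheduled visits out of summary tables and figures unless stated otherwise. The laboratory rules in section 11.5.3 use the scheduled value in summaries when a visit has several. Neither addresses derivation of baseline, and section 11.4.1.1 does not say whether it overrides them. Two programmers could reach different baselines.

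**Effect on the classes.** The SAP states no figure to reproduce here. Inputs:
- Cut-offs from section 2.5: 7-day classes change at 30% and 70%; 3-day classes at 10% and 20% per day, that is 30% and 60% in total over three days.
- r = pre-operative creatinine / screening creatinine. This is an assumption, shown from 0.5 to 1.5.
- True fall = fall measured from the pre-operative value.

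With screening creatinine S, the pre-operative value is rS and the later value is rS × (1 − true fall). Against screening:

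measured fall = 1 − r × (1 − true fall)

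| r | True fall | Measured fall | 7-day class: true → as read |
|---|---|---|---|
| 0.5 | 50% | 1 − 0.5 × 0.50 = 75% | intermediate → immediate |
| 0.6 | 10% | 1 − 0.6 × 0.90 = 46% | functional DGF → intermediate |
| 0.7 | 0% | 1 − 0.7 × 1.00 = 30% | functional DGF → intermediate |
| 0.8 | 20% | 1 − 0.8 × 0.80 = 36% | functional DGF → intermediate |
| 0.9 | 25% | 1 − 0.9 × 0.75 = 32.5% | functional DGF → intermediate |
| 1.0 | any | equals true fall | no change |
| 1.25 | 35% | 1 − 1.25 × 0.65 = 18.75% | intermediate → functional DGF |
| 1.5 | 50% | 1 − 1.5 × 0.50 = 25% | intermediate → functional DGF |

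The 3-day classes move the same way in these rows. At r = 0.7, for instance, 30% / 3 = 10% per day, the lower edge of intermediate.

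**Condition.** Every row that ends in intermediate or immediate requires no dialysis after transplantation, because section 2.5 restricts those classes to subjects without it.

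**How small a change matters.** The true fall that reads as exactly 30% is 1 − 0.7/r: 12.5% at r = 0.8, 22.2% at r = 0.9, 30% at r = 1 and 44% at r = 1.25.

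**The case against.** The rule says latest pre-dose assessment, not latest scheduled visit. The schedule also marks chemistry in the Unscheduled Visit column, so a routine pre-operative result recorded there could be baseline as the text stands. This is fair. A reader might infer that baseline creatinine always is the screening value; the document supports only that it is the sole *scheduled* one. The ambiguity remains, because the SAP never says such a result qualifies and its other rules favour scheduled values.

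The screening window and local laboratory practice may be set in the protocol, which is not at hand. If screening and surgery are close together with no dialysis between them, r is near 1 and little changes. That stands, and it is why no frequency is claimed.

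A reader might also infer that the results are tilted toward the drug. Dialysis after the screening sample (r < 1) does tilt them that way, but a rise after screening (r > 1) does the opposite. With no frequencies in the SAP, the net direction cannot be stated.

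Nor does every derived quantity divide by baseline. Absolute change subtracts it (section 11.4.1.2). The half-life takes half of its starting value as a target, and for DGF patients that starting value is taken after dialysis has finished, not at baseline.

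**Conclusion.** The point holds for secondary, descriptive endpoints. Followed as written, the schedule and the baseline rule can put a subject in the wrong graft-function class. A 30% drop in creatinine between screening and surgery (r = 0.7) is enough for a graft with no true fall to read as intermediate, given no post-transplant dialysis. A 25% rise (r = 1.25) turns a true 35% fall into functional DGF. These sizes rest on assumed values of r; how often they would occur cannot be worked out from the SAP.

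A reader might take this as a threat to the main result. It is not. The primary DGF endpoint and the sequential go/no-go rule rest on dialysis, and primary non function is declared by the site; none uses baseline creatinine. The matter should be settled before the creatinine tables are programmed.

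**What to change.** 1. Reconcile Appendix 2 with section 11.4.1.1: add creatinine to the pre-operative column, measured on the blood already drawn there before infusion.
2. Define baseline creatinine as the last value before the start of infusion and, where available, after any pre-operative dialysis. The anchor should be the start of infusion, not reperfusion: infusion may begin pre-operatively, so a pre-reperfusion sample could be post-dose.
3. State that unscheduled or local pre-dose results count for this purpose, despite the summary rules in sections 11.4.2 and 11.5.3.
4. Use the dialysis data already collected to flag subjects dialysed between the baseline sample and surgery, and repeat Table 2.08 without them as a sensitivity analysis. This needs dialysis timing relative to the sample; the SAP does not show whether that is recorded.

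Cost: one added assay, which changes the schedule as well as the SAP wording, but no extra blood draw. With at most 30 subjects, the sensitivity set will be smaller and may be much smaller if pre-operative dialysis is common.
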